6.4 STUDY INTERVENTION/EXPERIMENTAL MANIPULATION ADHERENCE

Participants' adherence with study procedures will be tracked by attendance at intervention visits. All study visits are mandatory to remain an active participant. Adherence to attendance at Visits 2-4 will be ascertained from the NDURE visit note authored by the navigator that is available in the EMR. Adherence to attendance at Visits 1 and 5 will be ascertained from the REDCap data collection form. Adherence to attendance at visits 1-5 will be documented in the electronic Case Report Form (eCRF).

6.5 CONCOMITANT THERAPY

N/A

6.5.1 RESCUE THERAPY

N/A

7 STUDY INTERVENTION DISCONTINUATION AND PARTICIPANT DISCONTINUATION/WITHDRAWAL

7.1 DISCONTINUATION OF STUDY INTERVENTION/EXPERIMENTAL MANIPULATION

At subject, PI, or study team member request.

7.2 PARTICIPANT DISCONTINUATION/WITHDRAWAL FROM THE STUDY

Participants are free to withdraw from participation in the study at any time upon request. The investigators will seek to minimize participant discontinuation/withdrawal from the study (see Section 7.3, Lost to Follow-Up) except for safety reasons.

The investigator may discontinue a participant from the study for the following reasons:

- Significant study intervention non-compliance

- Lost-to-follow up; unable to contact subject (see **Section 7.3, Lost to Follow-Up**)
- Any event or medical condition or situation occurs such that continued collection of follow-up study data would not be in the best interest of the participant or might require an additional treatment that would confound the interpretation of the study
- The participant is expected to have surgery and then decides to pursue (1) nonsurgical treatment or (2) surgical treatment at a site not participating in the clinical trial
- PORT is expected based on the clinical TNM classification, but analysis of the pathology specimen after surgery demonstrates no indication for PORT per NCCN Guidelines (i.e., all of the following adverse features are absent: extranodal extension, positive margin, pT3 or pT4 primary, N2 or N3 nodal disease, nodal disease in levels IV or V, PNI, and LVI)

The date and reason for participant discontinuation or withdrawal from the study will be recorded in the eCRF.

The reason for participant discontinuation or withdrawal from the study will be recorded on the eCRF.

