5 STUDY POPULATION

5.1 INCLUSION CRITERIA

In order to be eligible to participate in this study, an individual must meet all of the following criteria:

Patient and disease characteristics

1. Age \geq 18 years at the time of screening
2. Self-identified white or AA race
3. Cytologically or pathologically confirmed SCC (or histologic variant) of the oral cavity, oropharynx (p16 positive, negative, or unknown), hypopharynx, larynx, unknown primary, paranasal sinuses, or nasal cavity.
 - a. In situations in which the patient fulfills all other inclusion criteria, but the biopsy shows SCC in-situ or moderate/severe dysplasia (without definitive evidence of invasive SCC), but the patient is scheduled to undergo curative intent surgery by the treating oncologic surgeon due to clinical suspicion of invasive SCC, the diagnosis of SCC-in situ or moderate/severe dysplasia is sufficient to full the pathologic diagnosis enrollment criterion.
4. American Joint Committee on Cancer (AJCC) clinical stage grouping III-IV (8th edition) for patients with SCC of the oral cavity, p16-negative oropharynx, hypopharynx, larynx, paranasal sinuses, and nasal cavity; or AJCC clinical stage grouping III-IV (7th edition) for patients with p16-positive SCC of the oropharynx or unknown primary.
 - a. At screening, AJCC clinical stage grouping should be determined based on a combination of physical exam, diagnostic evaluation with cross sectional imaging of the neck (computerized tomography (CT) and/or magnetic resonance imaging (MRI)) and/or 18-F-fluoro-deoxyglucose positron emission tomography (FDG PET) CT within 60 days
 - b. In situations in which the patient fulfills all other inclusion criteria but the biopsy shows SCC in-situ or moderate/severe dysplasia (without definitive evidence of invasive SCC), but would otherwise have an appropriate clinical stage grouping as defined in criterion 5, the diagnosis of SCC-in situ or moderate/severe dysplasia is sufficient to full the staging enrollment criterion.
5. No prior exposure to radiation therapy, with or without concurrent chemotherapy, for treatment of HNSCC in the definitive or adjuvant therapy settings

Surgery and adjuvant therapy eligibility

6. Plan for curative intent surgery at MUSC

- a. At screening, plan for curative intent surgical resection of the HNSCC at MUSC must be deemed likely by the treating surgeon and/or multidisciplinary tumor board, which must include a fellowship-trained head and neck oncologic surgeon.

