7. Plan for PORT (at MUSC or non-MUSC) with or without concurrent chemotherapy following curative intent surgery
 - a. At screening, plan for adjuvant therapy following curative intent surgical resection of the HNSCC at MUSC must be deemed likely by the treating surgeon and/or multidisciplinary tumor board, which must include a fellowship-trained head and neck oncologic surgeon, based on the clinical expectation of at least one of the following adverse features on final pathologic evaluation: extranodal extension (ENE), pT3 or pT4 primary, N1 or greater nodal disease, nodal disease in levels IV or V, perineural invasion (PNI), or lymphovascular invasion (LVI).

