9.3 POPULATIONS FOR ANALYSES

The safety analysis set (SAS) is composed of all patients enrolled who receive any part of either the NDURE or UC intervention. The SAS will be used to conduct all safety analyses. Patients will be analyzed based on the intervention received regardless of the assignment at randomization.

The PORT delay analysis set is composed of all patients enrolled in the trial who are:

1. Randomized to NDURE or UC
2. Receive curative intent surgery at MUSC
3. Have an indication for PORT per NCCN Guidelines based on the presence of at least one of the following adverse features on final pathologic evaluation: ENE, positive margin, pT3 or pT4 primary, at least pN1 nodal disease (per AJCC 8th edition for p16-ve non-oropharyngeal SCC or AJCC 7th edition for p16+ve oropharyngeal SCC), nodal disease in levels IV or V, PNI or LVI
4. Are alive for ≥ 6 weeks postoperatively.

Analysis will be performed based on assignment at randomization regardless of the intervention received (modified intent to treat). This analysis set will be used for analysis of the primary endpoint. The rationale for this definition of the PORT delay evaluable set is that eligibility, randomization, and delivery of a portion of the intervention occur prior to definitive treatment of the HNSCC. However, the primary endpoint is evaluable only for patients who undergo surgery for HNSCC, have an indication for adjuvant PORT (which can only be definitively known following surgical resection), and are alive for at least 6 weeks postoperatively. Therefore, we expect that a subset of patients who meet all eligibility criteria will be enrolled in the study, randomized to NDURE or UC, receive a portion of the intervention, but subsequently be non-evaluable for the primary endpoint when information becomes available later in the clinical course that cannot be known at the time of study enrollment and randomization (e.g., they (1) elect a non-surgical treatment option; (2) have no indication for PORT per NCCN Guidelines on final pathologic assessment; (3) have a mortality prior to 6 weeks postoperatively).

The Time-to-PORT (TTP) analysis set is composed of all patients enrolled in the trial who are:

1. Randomized to NDURE or UC
2. Receive curative intent surgery at MUSC

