3. Have an indication for PORT per NCCN Guidelines based on the presence of at least one of the following adverse features on final pathologic evaluation: ENE, positive margin, pT3 or pT4 primary, at least pN1 nodal disease (per AJCC 8th edition for p16-ve non-oropharyngeal SCC or AJCC 7th edition for p16+ve oropharyngeal SCC), nodal disease in levels IV or V, PNI or LVI

Analysis will be performed based on assignment at randomization regardless of the intervention received (modified intent to treat). This analysis set will be used for analysis of the secondary endpoint TTP.

The **treatment package time (TPT) analysis set** is the TTP analysis set restricted to patients who have initiated PORT.

The **full analysis set (FAS)** is the set of all trial participants who enroll and are eligible for the study. Patients who enroll but subsequently drop out prior to receiving any of the assigned intervention will be replaced. The FAS will be used for evaluation of the pre-surgical radiation consultation, and for secondary analyses of both the primary endpoint and secondary endpoints.

The **dental evaluation prior to surgery analysis set** will be the FAS restricted to patients who receive curative intent surgery at MUSC and are indicated for dental evaluation.

The **extraction of indicated teeth analysis set** is the subset of patients in the dental evaluation prior to surgery analysis set who are indicated for dental extractions prior to surgery.

The **time from surgery to PORT referral scheduling analysis set** and **time from surgery to appointment with radiation oncology analysis set** are equivalent to the TTP analysis set.

The **Per protocol set** is composed of all patients enrolled in the trial who have completed all 3 of the ENDURE intervention sessions as described in the protocol. This analysis set will be used for secondary analyses of both the primary endpoint and secondary endpoints.

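### Section 7.2 lets a patient whose only adverse feature is pN1 be discontinued as having no PORT indication, while section 9.3 keeps that patient in the primary analysis set, with no explicit rule for collecting the PORT date afterwards

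*Combined protocol and SAP*

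**What the plan says.** Section 7.2 lists grounds for ending participation, introduced by "The investigator may discontinue a participant from the study for the following reasons". One applies when PORT was expected from clinical staging but pathology shows no indication under NCCN Guidelines. It is spelled out as "all of the following adverse features are absent: extranodal extension, positive margin, pT3 or pT4 primary, N2 or N3 nodal disease", together with no level IV or V nodes, no PNI and no LVI. For a discontinued patient, 7.2 requires the date and the reason to be recorded.

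Section 9.3 requires a PORT indication under NCCN Guidelines for the PORT delay (primary) set and again for the TTP set. Both use the list that begins "ENE, positive margin, pT3 or pT4 primary, at least pN1 nodal disease" and ends with the same level IV/V, PNI and LVI entries. Patients are analysed as randomised, and discontinuation is not an exclusion. The rationale in 9.3 names as non-evaluable those who "have no indication for PORT per NCCN Guidelines on final pathologic assessment".

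Section 5.1, item 7a, lists the features expected at screening as "extranodal extension (ENE), pT3 or pT4 primary, N1 or greater nodal disease", again followed by level IV/V nodes, PNI and LVI.

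Section 4.2.4 follows patients for the primary and secondary endpoints for 365 days from surgery. Section 8.4.4 takes efficacy data from the EMR and, for care elsewhere, from records requested at the end of adjuvant therapy. Section 9.4.2 scores an evaluable patient with missing PORT delay status as delayed.

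**The concern.** One patient gets two answers to the same question. If pN1 is the only adverse feature, 7.2 says there is no PORT indication and permits discontinuation, while 9.3 says there is one and places the patient in the primary set. Since 9.3 treats patients without an indication as non-evaluable, the two definitions should match.

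What is at stake is the outcome value, because set membership does not change. The patient may leave the study soon after the pathology report. For PORT outside MUSC, the steps that establish the start date come later: a footnote to the section 1.3 schedule has the coordinator contact the patient no sooner than 8 weeks after surgery, and 8.4.4 requests records when adjuvant therapy ends. If neither is done because the patient is off study, the missing-data rule turns a timely start into a delay.

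**Working it through.** **Comparing the lists.** Sections 7.2 and 9.3 give the same seven features in the same order and differ in one.

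| Feature | 7.2 (discontinuation) | 9.3 (PORT delay and TTP sets) | 5.1 item 7a (screening) |
|---|---|---|---|
| ENE | yes | yes | yes |
| Positive margin | yes | yes | not listed |
| pT3 or pT4 | yes | yes | yes |
| Nodal category | **N2 or N3** | **pN1 or greater** | **N1 or greater** |
| Level IV or V nodes | yes | yes | yes |
| PNI | yes | yes | yes |
| LVI | yes | yes | yes |

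On the nodal entry, 5.1 and 9.3 agree and 7.2 is the outlier.

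**Following one patient.** Take a randomised patient with curative-intent surgery at MUSC, pN1 as the only feature, alive at 6 weeks.

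1. All the features named in 7.2 are absent, so discontinuation is permitted.
2. All four conditions for the PORT delay set in 9.3 are met, so the patient is evaluable in the randomised arm.
3. If the PORT date is known, status follows from the 42-day rule. If it is not, 9.4.2 gives delayed.
4. The score is wrong only if PORT in fact began by day 42. A patient who started later, or never started, has no timely start to lose.

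**The plan's own figure.** Section 9.2.2 states 83% power for 45% v 25% with 75 per arm, using a pooled Z-test at two-sided alpha 0.10.

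- Pooled rate = (0.45 + 0.25)/2 = 0.35
- Null SE = √(2 × 0.35 × 0.65/75) = 0.0779
- Alternative SE = √((0.45 × 0.55 + 0.25 × 0.75)/75) = 0.0762
- z = (0.20 − 1.645 × 0.0779)/0.0762 ≈ 0.94, giving power 82.7%

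The stated figure is reproduced. Aligning 7.2 with 9.3 leaves it unchanged.

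**Size per patient.** One timely patient scored as delayed moves that arm's rate by 1/75 = 1.33 percentage points. The documents do not say how many there would be. The range of 0 to 3 below is an assumption, starting from the planned 45% v 25%.

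| Timely patients scored delayed | Difference if NDURE only | Difference if usual care only | Difference if the same number in each arm |
|---|---|---|---|
| 0 | 20.0 | 20.0 | 20.0 |
| 1 | 18.7 | 21.3 | 20.0 |
| 2 | 17.3 | 22.7 | 20.0 |
| 3 | 16.0 | 24.0 | 20.0 |

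Entries are percentage points (20 ∓ k/75 × 100 for k patients). The direction depends on the arm in which the dates are lost, and nothing in the documents indicates which that would be.

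**The case against.** The strongest reply is that the harm needs a long chain. pN1 must be the only feature. The investigator must use a permissive rule, although 7.2 also says discontinuation is to be minimised. The patient, judged to have no indication, must still start PORT by day 42, outside MUSC, and the date must never be found. That stands, and it is why the effect is probably small.

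A second reply is that collection after discontinuation is already covered. Section 4.2.4 makes no exception for discontinued patients, 8.4.4 relies on records and not on visits, and analysis as randomised presupposes that outcomes are sought. This is a fair reading, so it would go too far to say that the plan stops collecting these dates. But it is not explicit. Stopping the intervention is handled separately in 7.1, and another ground in 7.2 speaks of continued follow-up data collection not being in the participant's interest, which suggests that discontinuation can end collection. The consent pages are not in the public text and may address this.

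Third, both sections defer to NCCN Guidelines, so the list in 7.2 may simply be a slip. Which list matches the guideline cannot be checked from the documents. The case for changing 7.2 rests on its disagreement with 5.1 and 9.3.

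Two stronger readings are tempting. One is a loss of power, which would need the share of patients who are pN1-only, discontinued and without a date; the documents give none of these. The other is that AJCC editions alter who is analysed: 7.2 names no edition, 8.3 records pathologic TNM in the 8th, and 9.3 specifies "at least pN1 nodal disease (per AJCC 8th edition for p16-ve non-oropharyngeal SCC or AJCC 7th edition for p16+ve oropharyngeal SCC". The threshold in 9.3 is any nodal disease from pN1 upward, and no patient has been identified whose status on that threshold differs by edition. No effect on either analysis set is shown.

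**Conclusion.** The inconsistency is real and lies in the current text. The discontinuation rule and the primary analysis set use different nodal thresholds for the same concept, and how to obtain the outcome of a patient caught between them is not stated explicitly. It is a minor point of incomplete harmonisation, not a deliberate design choice. Its size is unknown and probably small: 1.3 points in one arm's delay rate per misclassified patient, and no change in the difference if the numbers are equal across arms. This rests on 75 evaluable patients per arm, on the investigator actually using the rule, and on the absence of a post-discontinuation collection rule in the text available. The stated sample size and power are not in question.

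**What to change.** 1. In section 7.2, replace the N2 or N3 entry with at least pN1 nodal disease, matching 9.3.
2. Add to section 7.2: for every randomised patient who has curative-intent surgery at MUSC, the surgery date and PORT start date are still collected from MUSC and outside-facility records after discontinuation, unless consent for record review is withdrawn.

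Section 9.4.2 can stay as it is, and no change to AJCC edition wording in 7.2, 8.3 or 9.3 is called for on this point. The cost is two short edits to 7.2 and a few outside-record requests.

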7.3 LOST TO FOLLOW-UP

A participant will be considered lost to follow-up if he or she fails to return for two scheduled visits and study staff are unable to contact the participant after at least 3 attempts.

The following actions must be taken if a participant fails to return to the clinic for a required study visit:

- The site will attempt to contact the participant, reschedule the missed visit within 2 weeks, counsel the participant on the importance of maintaining the assigned visit schedule and ascertain if the participant wishes to and/or should continue in the study
- Before a participant is deemed lost to follow-up, the investigator or designee will make every effort to regain contact with the participant (where possible, 3 telephone calls and, if necessary, a certified letter to the participant's last known mailing address or local equivalent methods). These contact attempts will be documented in the participant's medical record or study file.
- Should the participant continue to be unreachable, he or she will be considered to have withdrawn from the study with a primary reason of lost to follow-up.

8 STUDY ASSESSMENTS AND PROCEDURES

8.1 SCREENING PROCEDURES

Once a subject has signed the ICF, an identification number will be assigned to him/her and the study related screening procedures will start. A subject will be randomized into the study after he/she has signed the ICF and all eligibility criteria have been met.

8.2 BASELINE ASSESSMENTS

8.2.1 DEMOGRAPHIC

Demographic information is gathered as patient self-report using the Behavioral Risk Factor Surveillance Survey (BRFSS) Demographics.

BRFSS Demographics is the nation's premier health-related survey that collects data about health-related risk behaviors from US residents. The demographic section from the BRFSS will be used (in-person) to ascertain participant sex, age, race, marital status, insurance, educational attainment, living situation, zipcode, phones for personal use, employment, and annual household income⁴⁶.

8.2.2 CLINICAL AND ONCOLOGIC

Clinical and oncologic characteristics are assessed using clinical documentation within the EMR unless otherwise indicated.

Baseline oncologic characteristics include date of diagnosis, head and neck tumor subsite, tumor histology, p16/human papillomavirus (HPV) tumor status, AJCC 8th edition clinical TNM Class, AJCC 8th edition overall clinical stage grouping, and predicted facility delivering adjuvant therapy. In subjects with OPC or carcinoma of unknown primary, HPV status will be determined by p16 IHC, as determined by the participant's cytology or pathology report. Tumor staging is established using the AJCC/TNM Staging system, 8th edition based on clinical staging information from the treating provider (which includes history, physical exam, fiberoptic endoscopy [as indicated] and radiologic imaging (including CT or MRI and PET/CT). The predicted PORT facility, a stratification variable for randomization, is ascertained by the program coordinator based on discussions by the program coordinator with a treating clinician and potential participant.

8.2.3 RISK OF PORT DELAY

The risk of PORT delay is assessed using the Presurgical Nomograms for Predicting Delayed Postoperative Radiotherapy Initiation in Head and Neck Squamous Cell Carcinoma⁴⁰. The nomogram is a validated risk-prediction tool to estimate a personalized pre-treatment risk of PORT delay that is calculated based on the following baseline information available in the EMR: AJCC overall clinical stage grouping, head and neck subsite, insurance coverage, race and ethnicity, and Charlson/Deyo comorbidity score.

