1.3 SCHEDULE OF ACTIVITIES

Table 1. Schedule of Activities for NDURE and Usual Care: Screening, Treatment, and Follow-up								
Study Period		Screening	Allocation	Treatment			Follow-Up	
Visit Label	Visit #			Pre -Op	Pre - D/ C	Post - D/C		
Visit Label	Visit #	1	--	2	3 ^{a,b}	4 ^c	5 ^d	6 ^e
Study Activity								
Enrollment	Eligibility Screen	X						
	Informed Consent	X						
Allocation	Allocation		X					
Study Intervention	NDURE			X	X	X	X	
	Usual Care			X	X	X	X	
Study Assessments								
Baseline	Demographics	X						
	Baseline Oncologic Characteristics	X						
	Charlson-Deyo Comorbidity Index	X						
	PORT Delay Nomogram	X						
	Lukwago Cultural Questionnaire	X						
Safety	Adverse Events			←		→		
Efficacy	Surgical Details				X			
	PORT Start Date						X	
Fidelity	NDURE Fidelity						X	
Feasibility	NDURE Accrual	X						
	NDURE Completion			X	X	X	X	
	Navigator Caseload			←		→		
	Navigator Time Allocation			X	X	X	X	
Acceptability	PSN-I Questionnaire						X	
	Semi-Structured Interview						X	
	Program Evaluation Questionnaire						X	
Barriers to Timely PORT	PBQ-Patient Questionnaire			X	X	X	X	
	PBQ-Navigator			X	X	X	X	
	Presurgical RT Consult						X	
	Pre-RT Dental Extractions						X	

Table 1. Schedule of Activities for NDURE and Usual Care: Screening, Treatment, and Follow-up								
Study Period		Screening	Allocation	Treatment			Follow-Up	
Visit Label	Visit #			Pre-Op	Pre-D/C	Post-D/C		
		1	—	2	3 ^{a,b}	4 ^c	5 ^d	6 ^e
Study Activity								
Cancer Care Delivery Processes	Date Pathology Report Returned						X	
	Date of Postoperative Referral to Radiation Oncology						X	
	Date of Postop Appointment with Radiation Oncology						X	
	Date of CT Simulation						X	
Adjuvant Therapy Details	Type of Adjuvant Therapy						X	
	PORT Completion Date						X	
	Radiation and Medical Oncology Facility						X	
Health Behavior Constructs	CTM-15 Questionnaire				X	X		
	ISEL-12 Questionnaire	X					X	
	PSQ Questionnaire	X			X	X		
	IPQ-R Consequences Questionnaire	X			X	X		
	CASE-Cancer Questionnaire	X					X	

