8.4.4 EFFICACY ASSESSMENTS

Data for the efficacy assessments described below are gathered from the EMR. For participants who receive care at a non-MUSC facility (and thus whose information is not in the MUSC EMR), records will be requested for the treating facility at the conclusion of adjuvant therapy and scanned into MUSC EMR.

PORT Delay: The initiation of PORT more than 6 weeks (42 calendar days) from the date of the definitive surgical resection.

- If the surgical management of the primary tumor and the neck are staged (i.e. occur on two different calendar days), the date of the definitive surgery for the primary tumor will be used.
- If additional surgical resection is required (e.g. re-resection of positive margins to clear residual disease), the date of the earlier (i.e. attempted definitive) surgical procedure will be used to determine the date of definitive surgical resection.
- Patients who suffer a mortality prior to initiating PORT and > 6 weeks after surgery will be assessed as having a PORT delay.

- Patients who suffer a mortality prior to initiating PORT and \leq 6 weeks after surgery will be non-evaluable for evaluation of the primary endpoint of PORT delay.
- Patients who recur prior to initiating PORT, regardless of the timing of the recurrence relative to 6 weeks postoperatively, will be assessed equivalently to patients who do not recur for the purposes of this endpoint.

Time-to-PORT (TTP): The time, in days, between the date of definitive surgical resection to the initiation of PORT. All of the criteria used to adjudicate the date of the definitive surgical procedure described for the primary outcome measure will be applied to this measure.

- For patients who are alive and have not initiated PORT by 18 weeks (126 days) from surgery, TTP will be censored at this timepoint.
- For patients who suffer a mortality prior to initiating PORT and $<$ 18 weeks after surgery, TTP will be censored at the date of death. (A sensitivity analysis treating death as a competing risk will be performed, as described in Section 9.4)
- For patients who recur prior to initiating PORT, regardless of the timing of the recurrence relative to 18 weeks postoperatively, TTP will be assessed equivalently to patients who do not recur.

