trial arms will be analyzed using a model-based approach (discussed in Section 9.4.3.2) with inclusion of randomization stratification variables as model covariates, an analytic approach which preserves the type I error rate at nominal α , and increases power relative to an unadjusted model.⁶¹ Therefore, our power analysis based on a Z-test is conservative, and we anticipate even greater power based on our analytic plan. We therefore consider our RCT to be appropriately and rigorously designed to detect a clinically meaningful reduction in PORT delay. In order to have 150 patients eligible for the PORT delay analysis set (see Section 9.3, Population for Analyses), we plan to enroll 170 patients. Our sample size is inflated by 17% based on historical data. If at 170 patient accruals we have not achieved 75 patients evaluable for the primary endpoint in each arm, we will continue to enroll until we have achieved either accrual of a minimum of 75 evaluable patients in each arm or have accrued a maximum of 180 total patients.

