9.4.3.2 RCT OF NDURE VERSUS USUAL CARE

For the primary endpoint (delays starting PORT as defined in **Section 8.4, Endpoint and Other Non-Safety Assessments**), the difference in PORT delay comparing NDURE to UC will be evaluated using a model-based approach to accommodate adjustment for randomization stratification variables. Specifically, we will use a binary regression generalized linear model (GLM) with identity link to model the probability of PORT delay as a function of treatment arm and randomization stratification variables (race and predicted location of radiation facility). We adopt this approach as opposed to a logit model or Mantel-Haenzel (MH) type approach since the estimand is the population average treatment effect, whereas the odds ratio is not collapsable and therefore inference based on logistic regression or MH estimation would be limited to a conditional treatment effect. (Additional details can be found in the FDA Guidance Document on Adjusting for Covariates in Randomized Clinical Trials.) The risk difference (PORT delay rate in UC – PORT delay rate in NDURE) will be estimated based on the treatment effect slope parameter. We will report the corresponding model-based 90% CI and two-sided p-value. We will additionally report model-based PORT delay rates for each trial arm with corresponding 90% CIs. Should GLM convergence be an issue, we will adopt an alternative approach based on subject-level predicted probabilities of PORT delay from a logistic model as outlined by Freedman⁶² and by Steingrimsson.⁶³ Analysis will be performed using the PORT delay analysis set.

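### The baseline nomogram risk of PORT delay is collected in both arms but used in no analysis; pre-specifying it as a covariate in the primary model is a cheap improvement of uncertain size.

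*Combined protocol and SAP*

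**What the plan says.** Section 8.2.3 describes the score: "The nomogram is a validated risk-prediction tool to estimate a personalized pre-treatment risk of PORT delay". Its inputs are "AJCC overall clinical stage grouping, head and neck subsite, insurance coverage, race and ethnicity, and Charlson/Deyo comorbidity score". Table 1 in Section 1.3, which covers both NDURE and usual care, lists "PORT Delay Nomogram" among the baseline assessments at the screening visit, ahead of allocation.

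The primary endpoint in Section 8.4.4 is "The initiation of PORT more than 6 weeks (42 calendar days) from the date of the definitive surgical resection". Section 9.4.3.2 fits an identity-link binary regression, whose stated purpose is "to model the probability of PORT delay as a function of treatment arm and randomization stratification variables". Those variables are race and predicted radiation facility. If that model does not converge, the plan falls back on predicted probabilities from a logistic model.

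Section 9.2.2 defends covariate adjustment on the ground that it "increases power relative to an unadjusted model". The nomogram appears nowhere in Section 9. Its only other role is in the intervention (Section 6.1.1.1), where the navigator shows each NDURE patient a personal risk estimate.

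**The concern.** The plan accepts that adjusting for baseline prognostic variables helps, then stops at the two design variables. It already schedules a score aimed at the event it wants to compare. That score carries information on stage, subsite, insurance and comorbidity, none of which is in the model. Section 9.4.7 itself calls insurance a risk factor for delay that could confound a future trial if imbalanced.

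With 75 evaluable patients per arm, chance imbalance in such factors is plausible, and a prognostic covariate both guards against it and narrows the interval for the risk difference. At stake is some precision in an estimate meant to inform a definitive trial. The validity of the result is not in question.

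**Working it through.** **1. Reproduce the stated power (Section 9.2.2).** Inputs: 75 per arm, 45% versus 25%, two-sided alpha 0.10, pooled Z-test.

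- Pooled SE = sqrt(2 × 0.35 × 0.65 / 75) = 0.0779; critical difference = 1.645 × 0.0779 = 0.1281.
- Unpooled SE = sqrt((0.45 × 0.55 + 0.25 × 0.75) / 75) = 0.0762.
- Power = Φ((0.20 − 0.1281) / 0.0762) = Φ(0.944) = 82.7%, against 83% stated.

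**2. Approximate value of the score.** Let R² be the extra outcome variance it explains beyond arm, race and facility (assumed, since the documents give none). Effective n per arm = 75 / (1 − R²); 90% CI half-width = 1.645 × 0.0762 × sqrt(1 − R²).

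| Extra R² | Power | CI half-width (points) | Equivalent total N |
|---|---|---|---|
| 0 | 82.7% | 12.5 | 150 |
| 0.02 | 83.4% | 12.4 | 153 |
| 0.05 | 84.4% | 12.2 | 158 |
| 0.10 | 86.1% | 11.9 | 167 |
| 0.15 | 87.8% | 11.6 | 176 |

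**3. Simulation against the right comparator.** The comparator is the model that already holds race and facility. There were 6,000 trials per scenario with N = 150 (50 AA and 100 white, Section 5.5), delay rates of 45% and 25%, and standardised logistic risk differences with and without the score. Assumptions not in the documents: race log-odds ratio 0.45, facility log-odds ratio 0.6, half of patients at each facility type, and a normally distributed non-race part of the score. AUC is for the score including race. The variance ratio is strata-only over strata plus score, so values above 1 favour the score.

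| Assumed AUC | Variance ratio | Power, strata only → with score | Valid identity-link fit with score |
|---|---|---|---|
| 0.55 (nothing beyond race) | 0.99 | 83.4 → 83.5% | 85% |
| 0.60 | 1.01 | 84.2 → 84.6% | 62% |
| 0.64 | 1.04 | 83.8 → 85.3% | 31% |
| 0.68 | 1.10 | 84.1 → 87.0% | 11% |
| 0.72 | 1.12 | 84.2 → 87.9% | 2% |
| 0.77 | 1.24 | 83.6 → 90.4% | 0.4% |

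Each simulated power has a standard error of about sqrt(0.84 × 0.16 / 6000) = 0.5 points. With the score included, type I error was 9.5 to 10.6% against a nominal 10%.

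The last column comes from 500 identity-link fits per scenario and counts those that converged with all fitted risks between 0 and 1. With the two strata only, 99 to 100% were valid. These rates depend on the fitting algorithm and on the normal-score assumption.

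**The case against.** The strongest reply is that nothing here is defective. The model adjusts for both design variables and targets a marginal risk difference, and its power already exceeds the 80% target without the score. Imbalance is partly covered by stratification on facility, fixed AA numbers per arm, and a planned subset analysis by insurance. All of that stands, which is why this is an improvement and not an error.

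The gain is also uncertain. No AUC, R² or calibration is given. Race is already in the model, Hispanic patients are excluded and clinical stage is limited to III–IV, all of which may shrink what the score adds. This stands too.

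A reader might infer more than the documents support:

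- **That precision is being given up at no cost.** A continuous score in the identity-link model often yields no valid fit, so using it well means changing the primary estimator. The gain could be nil.
- **That the score predicts exactly this endpoint.** Section 8.2.3 states no delay cut-off. The trial counts deaths beyond six weeks before PORT (Section 8.4.4) and missing status (Section 9.4.2) as delay; nothing shows that the nomogram did.
- **That every patient will have it.** The schedule plans this; completeness is not documented.
- **That the gain can be read off the unadjusted Z-test.** Using the score's whole R² (0.029, 0.064, 0.112 at assumed AUC 0.60, 0.65, 0.70) gives 77, 80 and 84 per arm and power of 83.7, 84.9 and 86.5%. That credits the score with what race already explains. At 0.60 the simulated gain is 0.4 points, not 1.0.

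Timing matters as well. The trial is unblinded, and Section 10.1.6 has the principal investigator reviewing endpoint data monthly, without saying whether by arm. A late change to the primary model would lose credibility.

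None of this undoes the case for acting. The score is a baseline variable even though only NDURE patients are told theirs, so adjusting for it is valid, and the loss if it proves useless is about 1% in variance.

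**Conclusion.** The point holds as a missed efficiency. A baseline risk score for PORT delay is scheduled in both arms and left out of every analysis, although the plan itself argues that adjustment raises power. The stated analysis remains valid and its 83% power reproduces.

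Beyond race and facility, the expected gain is about 0 to 1.5 power points for an assumed AUC of 0.55 to 0.64 and about 3 to 4 points for 0.68 to 0.72. An AUC of 0.77 would give about 7. These figures rest on assumed discrimination and the simulation settings above; the documents cannot narrow the range.

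**What to change.** Before outcomes are reviewed by arm, amend Section 9.4.3.2 to:

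1. Add the nomogram-predicted risk, on the logit scale, as a covariate alongside race and facility.
2. Make the standardised logistic estimator, now the fallback, the main one: risk difference = mean over all analysed patients of (predicted risk under UC − predicted risk under NDURE). This keeps the marginal estimand. State the standard-error method.
3. Keep the strata-only identity-link model as a sensitivity analysis.
4. Give a rule for missing score components; Section 9.4.2 has none for baseline covariates.
5. Say which nomogram is used (Section 8.2.3 refers to them in the plural) and which AJCC edition feeds it. Section 5.1 uses the 7th edition for p16-positive oropharyngeal or unknown-primary disease, Section 8.2.2 records the 8th, and Section 8.2.3 is silent.

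Cost: SAP wording only, with no new visits, patients or data items. The downsides are the change of primary estimator, the extra rules and a possibly nil gain.
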